9.3.10 Disease Assessment

Patients will be assessed for disease response according to the European Group for Blood and Marrow Transplant criteria, modified and updated by the IMWG criteria (Appendix F).

For Parts 1 and 2, response assessments will be made on the basis of local laboratory data. For Part 3, response assessments will be made on the basis of central laboratory data.

Assessments should occur every cycle during treatment and every 4 weeks during the PFS/survival follow up period until disease progression (see SOEs). If the start of a cycle is delayed, serum M-protein and serum FLCs are to be collected for central laboratory analysis if not previously sent within the preceding 10 days. If a patient has collected a 24-hour urine sample and brought it to a visit, the sample should be sent for central laboratory analysis of urine M-protein even if not on Day 1 of a cycle.

Serum and urine response assessments will be performed as indicated in the SOEs (Appendix A). Imaging tests for qualifying patients (see Sections 9.3.10.1 and 9.3.10.2) are to be performed every other cycle beginning with Cycle 3 only for patients with extramedullary disease at screening or when there is a clinical suspicion of extramedullary progression. In extenuating circumstances, such as during the COVID-19 public health emergency, patients may use an alternative site for imaging with prior notification to the sponsor or designee.

CR should be confirmed follow up assessments (by local laboratories for Parts 1 and 2 and by central laboratories for Part 3) of serum protein electrophoresis (SPEP), urine protein electrophoresis (UPEP), immunofixation of blood and urine, and serum FLCs as outlined in the SOEs (Appendix A). One bone marrow assessment (locally evaluated for Parts 1, 2 and 3) is required to document CR; no second bone marrow confirmation is needed.

Please note that to determine a response of sCR, bone marrow immunohistochemistry or immunofluorescence for the κ : λ ratio, as well as serum FLC assay, should be performed for all patients suspected to be in CR to meet this response category's requirements.

For Parts 1 and 2, PD may be confirmed per standard clinical practice at the site. Local laboratories may be used to confirm PD. For Part 3, PD must be confirmed based on central laboratories.

The following disease assessments will be performed as indicated in the SOEs (Appendix A).

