- Schedule D: Modakafusp alfa infusions will be administered on a 28-day (4-week) cycle once every 4 weeks until treatment discontinuation criterion is met.

During the dose escalation phase and after the first cycle, patients who have not experienced a DLT, have not shown signs of progressive disease (PD), and in the opinion of the investigator would continue to benefit from additional modakafusp alfa, may receive additional cycles of treatment. A window of ± 2 days will be permitted for the weekly and every-2-week doses, and a window of ± 4 days will be permitted for the every 3-week and every 4-week doses.

Part 2 Dose Expansion

The primary objective of Part 2 of the study is to provide a preliminary evaluation of the clinical activity of one or more schedules of modakafusp alfa given as a single agent in patients with RRMM. Additional cohort(s) of modakafusp alfa (using the same dose used in a single-agent cohort) in combination with dexamethasone will be implemented, with the selected schedule(s)

to be determined once the modakafusp alfa MTD or OBD is established. Treatment allocation will be assigned based on patient availability and eligibility. Dexamethasone will be given as a once weekly oral dose of 40 mg. Patients over 75 years of age will receive a reduced dose of dexamethasone (20 mg, same schedule). The aim of this approach is to obtain preliminary information on the effect of standard doses of dexamethasone on modakafusp alfa safety, efficacy, and pharmacodynamic endpoints.

Preliminary activity of modakafusp alfa as a single agent and in combination with dexamethasone will be evaluated by measuring the confirmed ORR (partial response [PR] or better) according to IMWG Uniform Response Criteria (Protocol Appendix F). The efficacy of modakafusp alfa will further assessed by assessing DOR, PFS, OS, and time to response.

Part 3 Dose Extension

Part 3 will determine the confirmed ORR per IRC assessment, evaluate other efficacy endpoints, assess MRD negativity in patients achieving CR, further characterize the safety, tolerability, and immunogenicity of modakafusp alfa therapy, collect PK data, and assess healthcare resource utilization.

The modakafusp alfa doses of 1.5 mg/kg and 3 mg/kg Q4W will be translated into 2 fixed doses of 120 mg and 240 mg based on the median bodyweight of approximately 80 kg (from Parts 1 and 2 of Study TAK-573-1501) for the Part 3 evaluation.

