7.1.4 Extended Loss-to-Follow-up

For subjects, if two or more scheduled disease assessments are missed and are then followed by an assessment of PD or death, PFS, DOR, and TTP will be censored at the last adequate assessment prior to PD or death. If the scheduled disease assessment is every 4 weeks (Schedule A, B, and D), a window of 64 days will be used to determine whether there was an extended time without adequate assessment. That is, if the time difference between PD/death and last adequate assessment is more than 64 days, then PFS, DOR and TTP will be censored at the last adequate assessment prior to PD/death. If the scheduled disease assessment is every 3 weeks (Schedule C), a window of 50 days will be used to determine whether there was an extended time without adequate assessment.

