Duration of disease control is defined as the time from first documented evidence of SD or better until the earliest date of a confirmed PD per IMWG, or death among patients who achieve a SD or better. Patients without confirmed PD or death will be censored at the censoring time point for PFS as specified in Table 1.

Duration of disease control will be analyzed at the time of primary ORR analysis, also at final analysis (study close out), based on responses assessed by both IRC and investigator.

Duration of disease control will be summarized using the Kaplan-Meier method by dose level for patients with a SD or confirmed MR or better. Median duration of disease control, first and third quartiles and 95% CI, will be estimated using the Brookmeyer-Crowley method.

PFS

PFS is defined as the time from the date of first dose until the earliest date of confirmed PD per IMWG, or death due to any cause. PFS will be analyzed at the time of primary analysis of ORR, also at final analysis (study close out), based on responses assessed by both IRC and investigator.

A summary of the assignments for progression and censoring dates for PFS are specified in Table 1 below.

Table 1 Assignments for Progression and Censoring Date for PFS Analysis

Scenarios	Event date/censoring date	Event status
No (or inadequate) baseline tumor assessments ¹	Date of the first dose	Censored
No post-baseline assessments	Date of the first dose	Censored
Confirmed progression documented without extended loss-to-follow-up time (two or more missed cycles) ⁴	Date of assessment of the earliest date of the confirmed progression	Event
No confirmed progression or death	Date of last adequate assessment of response ²	Censored
Subsequent anti-cancer therapy started (before documented confirmed progression or death) ³	Date of last adequate assessment of response ² (prior to the initiation of the subsequent anti-cancer therapy)	Censored
Death without extended loss-to-follow-up time	Death date	Event
Death or progression after an extended loss-to-follow-up time (two or more missed cycles) ⁴	Date of last adequate assessment of response ² (prior to missed assessments)	Censored

1. Adequate baseline assessment is defined as at baseline, a patient has at least one of the following measurements:
 - a. Serum M-protein $\geq 0.5\text{g/dL}$ ($\geq 500\text{ mg/dL}$) or
 - b. Urine M-protein $\geq 200\text{ mg/24 hours}$ or

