 - c. Serum FLC assay: Involved FLC level $\geq 10\text{ mg/dL}$ ($\geq 100\text{ mg/L}$) and an abnormal serum FLC ratio (<0.26 or >1.65)
2. An adequate assessment is defined as an assessment where the IRC/investigator determined response is sCR, CR, VGPR, PR, MR, or SD prior to a subsequent anti-cancer therapy. An unconfirmed PD assessment is also considered as an adequate assessment.
3. If PD or death and the subsequent anti-cancer therapy occur on the same day, it is assumed that the progression or death was documented first (e.g., event status is an event, and the date of event is the date of progression or death). If the subsequent anti-cancer therapy is initiated prior to any adequate assessment, censoring date should be the date of the first dose.
4. Refer to Section 7.1.4 “Extended Loss-to-follow-up”

PFS will be summarized using the Kaplan-Meier method by dose level. Median PFS, first and third quartiles, 3-month, 6-month, 9-month, 12-month PFS rate (or later time points if data

permits), and 95% CIs will be estimated using the Brookmeyer-Crowley method. A Kaplan-Meier plot of PFS time will also be provided.

TTP

TTP is defined as the time from the date of the first dose until the earliest date of confirmed PD per IMWG.

TTP will be analyzed at the time of primary analysis of ORR, also at final analysis (study close out), based on responses assessed by both IRC and investigator.

A summary of the assignments for progression and censoring dates for TTP are specified in Table 2.

Table 2 Assignments for Progression and Censoring Date for TTP Analysis

Scenarios	Event date/censoring date	Event status
No (or inadequate) baseline tumor assessments ¹	Date of the first dose	Censored
No post-baseline assessments	Date of the first dose	Censored
Confirmed progression documented without extended loss-to-follow-up time (two or more missed cycles) ⁴	Date of assessment of the earliest date of the confirmed progression	Event
No confirmed progression or death	Date of last adequate assessment of response ²	Censored
Subsequent anti-cancer therapy started (before documented confirmed progression) ³	Date of last adequate assessment of response ² (on or prior to the initiation of the subsequent anti-cancer therapy)	Censored
Death	Date of last adequate assessment of response ² prior to death	Censored

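### The 64/50-day limits in SAP 7.1.4 match the two-missed-assessments principle only on treatment; after a stop without progression they can censor an event when no visit, or only one, was missed (minor)

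*SAP*

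**What the plan says.** SAP 7.1.4 states the principle first: PFS, DOR and TTP are censored at the last adequate assessment "if two or more scheduled disease assessments are missed and are then followed by an assessment of PD or death". It then turns this into elapsed time. For 4-weekly assessment (Schedules A, B and D), "a window of 64 days will be used to determine whether there was an extended time without adequate assessment", and a longer gap is censored. For Schedule C the limit is 50 days. No separate limit is given for the period after treatment.

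Table 1 (SAP 7.8.2.2) repeats the principle as a count. It censors "Death or progression after an extended loss-to-follow-up time (two or more missed cycles") and keeps as an event "Death without extended loss-to-follow-up time". Table 2 does the same for progression in TTP. Both refer back to 7.1.4. The durations of clinical benefit and disease control use the same table: "Patients without confirmed PD or death will be censored at the censoring time point for PFS as specified in Table 1". Table 1, note 2 says what resets the clock: "An adequate assessment is defined as an assessment where the IRC/investigator determined response is sCR, CR, VGPR, PR, MR, or SD".

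Protocol 9.3.10 sets the schedule: "Assessments should occur every cycle during treatment and every 4 weeks during the PFS/survival follow up period until disease progression". Protocol Appendix A (Tables 11 and 13) puts the EOT visit 30 (+10) days after the last dose if no new therapy starts sooner, and PFS visits every 4±1 weeks counted from EOT. The myeloma tests at EOT are marked conditional. The footnotes name progression and CR and, in Parts 1 and 2, completion of treatment.

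**The concern.** The count and the day limit should classify the same patient in the same way. After EOT they need not, because EOT adds 30 to 40 days before the 4-weekly clock restarts and a disease rating at EOT is not always required. Where they differ, a programmer following the day limit turns a real event into a censored time, and the stated principle would have kept the event. The error runs in one direction and falls on patients who stopped for reasons other than progression. The endpoints at stake are PFS, DOR, TTP (through progression only, since TTP censors deaths anyway) and the two durations that borrow Table 1.

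**Working it through.** **1. Where 64 and 50 come from.** The SAP does not say. SAP 4.4 allows ±4 "days will be permitted for the every 3-week and every 4-week doses". With one visit missed, the longest on-treatment gap is 2 × interval + 2 × 4 days:
- 4-weekly: 2×28 + 8 = 64.
- 3-weekly: 2×21 + 8 = 50.

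Both match exactly. A ±2-day window would give 60 and 46. So the derivation is inferred, but it fits.

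**2. On treatment the limits work.**
- 4-weekly: one missed visit gives 48–64 days, two give 76–92.
- 3-weekly: one missed visit gives 34–50 days, two give 55–71.

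**3. Across EOT they do not.** Conditions: the stop is not for progression; the last adequate assessment is on the last dose day; there is no rating at EOT or in a held cycle; no new therapy starts. EOT is on day 30–40, and the nth PFS visit is at EOT + 28n ± 7 days.

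| PFS visits missed | Gap from last adequate assessment | Above 64 days |
|---|---|---|
| none | 30+21 = 51 to 40+35 = 75 (nominal 30+28 = 58) | 66 of 165 day pairs |
| one | 30+49 = 79 to 40+63 = 103 | 165 of 165 |
| two | 30+77 = 107 to 40+91 = 131 | all |

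The 165 pairs are 11 EOT days × 15 visit days. This counts windows; it is not a frequency. With EOT on day 30, 1 of 15 visit days exceeds the limit (30+35 = 65). With the visit exactly 28 days after EOT, the EOT days that exceed it are 37–40, which is 4 of 11.

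Deaths on days 65–75 are treated in the same way for PFS and DOR. The first PFS window closes between day 65 (EOT day 30) and day 75 (EOT day 40), so at most one visit has been missed by then.

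**4. Related cases.**
- Between two follow-up visits, one missed visit gives 56 ± 14 = 42–70 days; 21 of 225 offset pairs exceed 64.
- Schedule A (Cycles 3–6) and Schedule B (from Cycle 3) dose on Days 1 and 15, but the response tests are on Day 1 only (Protocol Appendix A, Tables 2, 4 and 5). Under the other conditions in step 3, a last dose on Day 15 adds 14 days: 51+14 = 65 to 75+14 = 89, with none missed. With ±2 days on both dosing visits the range is 61–93.
- For Schedule C, the SAP does not say whether 50 days still applies once follow-up is 4-weekly. If it does, every in-window first PFS visit (51–75) exceeds it.

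**5. What protects patients.**
- From a rated EOT visit, the first PFS visit is 21–35 days away, or 49–63 with one missed. All are below 64.
- From a rateable held-cycle sample on day 28 (Protocol 9.3.10), it is 51−28 = 23 to 75−28 = 47 days away.

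**6. Size, on assumed inputs.** The documents do not give the share of patients exposed. As an illustration, assume 118 patients per arm, exponential PFS with a median of 5 months, 15% of events being deaths, full attendance, no new therapy, and 5–15% of patients stopping at once in Cycles 1–4 for reasons other than progression.
- EOT always on day 30: about 0.1–0.2 events per arm become censored, and 6-month PFS rises by about 0.1 point or less.
- EOT spread evenly over days 30–40: about 0.4–1.3 events become censored, and 6-month PFS rises by 0.2–0.6 points.

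The standard error at 46% is √(0.46×0.54/118) = 4.6 points.

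**The case against.** - **The day limit is the definition.** 7.1.4 introduces it as a restatement of the principle, so programming is unambiguous, and Table 1 speaks of missed cycles rather than visits. It is true that the code would be deterministic. But the restatement is not equivalent to the principle after EOT, cycles have no meaning there, and no off-treatment limit is set.
- **The 30–40 day EOT range is generous.** Footnote aa to Protocol Appendix A Table 13, and its counterpart for Table 11, cap EOT laboratory tests at 30 days after the last dose. Protocol 6.3.1 and 8.4.4 also put the visit at 30 days. This stands: with EOT on day 30, only day 65 is censored with nothing missed. It does not help the patient who misses one visit, because even then the gap is at least 79 days.
- **Part 3 may be protected.** The investigator's status rating is scheduled unconditionally at EOT, and Part 3 responses rest on central laboratory data. If those samples are drawn to support the rating, the IRC has them too. Footnote z can be read as limiting repeat tests rather than dropping them after other stops, although the note on bracketed crosses points the other way. The exposure of IRC endpoints is therefore arguable.
- **Few patients qualify.** Protocol 4.6.2 says toxicity rarely led to discontinuation, and toxicity stops often follow a delay with sampling. This stands, and it is why the size above is only an illustration.
- **Schedule C.** 7.1.4 ties each limit to the assessment interval, so 64 days arguably applies once visits are 4-weekly. A reader might infer that every Schedule C patient is censored at the first PFS visit. The text does not settle that.

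**Conclusion.** The inconsistency is real and the severity is minor. As written, the day rule can censor progression at an in-window first PFS visit on days 65–75. Across EOT without a rating, it always censors an event found after one missed PFS visit, although the principle requires two. This depends on all the conditions in step 3 of the working. Exposure is mainly in Parts 1 and 2, where EOT tests are conditional and the EOT table has no investigator rating. It extends to Part 3 IRC-assessed endpoints only if EOT samples are not drawn after stops for reasons other than progression.

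A reader might infer that patients on the nominal schedule are censored, that 66 of 165 is the proportion affected, or that the PFS results are materially distorted. The documents support none of these. Nominal Schedule D timing gives day 58, actual visit timing and the exposed share are not reported, and the illustrated shift is well inside one standard error. The bias is upward and probably small, in descriptive secondary endpoints with no comparison between arms. The primary ORR does not use this rule.

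**What to change.** In SAP 7.1.4 and Tables 1 and 2, decide extended loss by counting the scheduled disease assessments actually missed (two or more). Count against the Schedule of Events for that part and that assessor, both on and off treatment. Apply the same rule to PFS, DOR, TTP and the durations of clinical benefit and disease control. If 64 and 50 days are kept at all, restrict them to gaps between on-treatment assessments.

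Longer day limits after EOT are not a good substitute. Between follow-up visits, one missed visit (42–70 days) and two (70–98 days) meet at day 70. Across EOT, a limit of 103 days would count a Part 3 investigator-assessed event after both the EOT rating and the first PFS visit were missed, which is two scheduled assessments.

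The cost is a wording change in the SAP and a change to the derivation. No new data are needed.

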7.2 Analysis Sets

Part 1 and Part 2

- Safety Analysis Set: The safety analysis set will include all enrolled patients who receive at least 1 dose of the study drug even an incomplete dose, of modakafusp alfa or Dexamethasone. The safety population will be used for safety related analyses such as AE, concomitant medications, laboratory tests, and vital signs. In addition, it will also be used for the efficacy analyses.
- Response-Evaluable Analysis Set: The subset of the safety analysis set of patients treated at the MTD/OBD from the Part 2 dose expansion cohorts with measurable disease at baseline and at least 1 post-treatment efficacy evaluation. The response-evaluable analysis set will be used in the futility analysis of the Part 2 expansion.
- DLT Evaluable Analysis Set: Patients who receive all Cycle 1 doses of modakafusp alfa or experience a DLT in Cycle 1 in the Part 1 dose escalation cohorts.
- Pharmacokinetic (PK) Analysis Set: The PK analysis set includes patients from the safety analysis set who have sufficient data to report at least 1 PK concentration for modakafusp alfa. The PK analysis set will be used for PK analysis.
- Immunogenicity-evaluable Analysis Set: The immunogenicity-evaluable analysis set will include patients from the safety analysis set with a baseline assessment and at least 1 post-baseline immunogenicity assessment. The immunogenicity-evaluable analysis set will be used for immunogenicity analysis.

Part 3

- Full Analysis Set (Safety Analysis Set): The full analysis set will include all enrolled patients who receive at least 1 dose of the study drug even an incomplete dose, of modakafusp alfa. The full analysis set will be used for baseline assessment, efficacy analysis and PRO compliance. The safety analysis set will be used for safety analysis.
- Intent-to-treat (ITT) Analysis Set: The ITT analysis set will include all randomized patients regardless of whether they receive study drug or adhere to the assigned dose. The ITT analysis set will be used for listings.
- Pharmacokinetic (PK) Analysis Set: The PK analysis set includes patients from the safety analysis set who have sufficient data to report at least 1 PK concentration for modakafusp alfa. The PK analysis set will be used for PK analysis.
- Immunogenicity-evaluable Analysis Set: The immunogenicity-evaluable analysis set will include patients with a baseline assessment and at least 1 post-baseline immunogenicity assessment. The immunogenicity-evaluable analysis set will be used for immunogenicity analysis.

- PRO Analysis Set: The PRO analysis set includes all patients with a baseline and at least one post-baseline measurement of any PRO. The analyses of PROs will be based on the PRO analysis set.

7.3 Disposition of Subjects

Study information, including the date first subject signed the informed consent form (ICF), date of last subject's last visit/contact, date of last subject's last procedure for collection of data for primary endpoint, MedDRA Version, WHO Drug Version, and SAS Version will be presented. The reasons for screen failures will be generated in a summary table.

The disposition includes the number and percentage of patients in the following categories: patients in each of the study populations, primary reason off treatment, ongoing (if applicable at the time of database lock/data cut-off), participating in PFS follow-up, and primary reason discontinued from the study. This information will be presented by safety analysis set in Part 1 escalation cohorts and Part 2 expansion cohorts and by full analysis set in Part 3 extension cohorts.

7.4 Demographic and Other Baseline Characteristics

All demographics and baseline characteristics will be summarized by safety analysis set in Part 1 escalation cohorts and Part 2 expansion cohorts and by full analysis set in Part 3 extension cohorts.

Demographics

Demographic data to be evaluated will include age, sex, race, ethnicity, height, and weight.

Stratification factors (Part 3 only)

- Type of Myeloma
 - IgA
 - Other
- Cytogenetic
 - High risk [(del17, t(4;14) and/or t(14;16)]
 - Standard risk

Disease characteristics:

- Years since initial diagnosis [(date of first dose – date of diagnosis) / 365.25)].
- Type of Myeloma
 - IgG, IgA, IgD, IgM, Biclonal (if known, otherwise summarize with Light chain below).

- Light Chain Kappa, Light Chain Lambda, Light chain Biclonal, Light Chain unknown.
- Measurable disease
 - Measurable by both SPEP (baseline serum M-protein ≥ 0.5 g/dL) and UPEP (baseline urine M-protein ≥ 200 mg/24 hr)
 - Measurable by SPEP only
 - Measurable by UPEP only
 - Measurable by FLC only (met all three criteria below):
 1. Involved either Kappa or Lambda free light chain level at baseline ≥ 10 mg/dL;
 2. and FLC ratio (Kappa FLC/Lambda FLC) is abnormal (serum FLC ratio > 1.65 or < 0.26)
 3. and not measurable by SPEP or UPEP
 - Non-measurable (not measurable by SPEP, UPEP, or FLC)
- Durie-Salmon Stage.
- International Staging System (ISS) at initial diagnosis.
- International Staging System (ISS) at study entry.
- Evidence of Lytic Bone Disease at initial diagnosis.
- Evidence of Extramedullary Disease at initial diagnosis.
- Eastern Cooperative Oncology Group (ECOG) performance status.

Baseline disease characteristics—laboratory values

- β_2 -microglobulin category (< 2.5 , $2.5-5.5$, > 5.5 mg/L).
- Serum albumin category (< 3.5 , ≥ 3.5 mg/dL).
- Serum creatinine category (≤ 2 , > 2 mg/dL).
- Calculated creatinine clearance category (< 30 , $30 - < 60$, $60 - < 90$, ≥ 90 mL/min).
Creatinine clearance will be calculated using the Cockcroft-Gault formulas as follows:

For male patients:

$$\text{creatinine clearance} = \frac{(140 - \text{Age[yrs]}) \times \text{weight[kg]}}{72 \times (\text{serum creatinine [mg/dL]})}$$

For female patients multiply by 0.85.

- Hemoglobin (g/L).
- Platelet count (10^9 /L).
- Absolute neutrophil count (10^9 /L).
- Lactate dehydrogenase (LDH) $>$ Upper limit of normal (ULN).

Baseline Bone Marrow Evaluation

- Baseline bone marrow aspirate/biopsy performed and adequate for interpretation.
- Percent plasma cells in bone marrow (if both biopsy and aspirate were performed use larger value; unable to detect is considered as zero).

Cytogenetics

- Cytogenetic testing performed.

The number and percentage of patients with each type of chromosomal aberration or abnormality will be presented including but not limited to the following:

- high risk cytogenetics [del 17, t(4;14) or t(14;16)].
- expanded high risk cytogenetics [del 17, t(4;14), (14;16), or 1q21 amplification/gain].
- del 13.
- del 17.
- t(4;14).
- t(11;14).
- t(14;16).
- t(14;20).
- 1q21 amplification/gain.
- hyperdiploidy.
- hypodiploidy.

(percentages are based on the number of patients with cytogenetic testing performed)

Extramedullary Disease Assessment (imaging)

- Imaging lytic lesions (yes, no, indeterminate).
- Imaging extramedullary plasmacytomas (yes, no indeterminate).
- Location of plasmacytomas (Liver, Visceral; Lung, Visceral; Node; Soft Tissue; Other).
- Number of plasmacytomas (1, 2, ≥ 3).
- Skeletal survey results (normal, abnormal not clinically significant, abnormal clinically significant, and not done).
- Skeletal survey lytic lesions (yes, no, indeterminate).

Prior therapy

- Prior radiation (yes).
- Prior surgery (yes).
- Prior bone marrow transplant or stem cell transplant.
 - Type of stem cell transplant (autologous, allogeneic, syngeneic, unknown).

- Prior systemic therapy (yes).
- Lines of prior therapy (descriptive statistics and categorical summary: 1, 2, 3, 4, 5, 6, >6).
- Lines of prior therapy initiated within 12 months of first dose of modakafusp alfa (categorical summary).
- Type of prior therapy may include but not limited to:
 - Anti-CD38 monoclonal antibody (Daratumumab, Isatuximab).
 - CAR-T.
 - Anti-BCMA.
 - IMiD.
 - Proteasome inhibitor (PI).
 - Elotuzumab.
- Type of last line of prior therapy.
- Best response to any prior anti-CD38.
- Best response to last line of prior therapy
- Refractory to prior therapy may include but not limited to:
 - Refractory to anti-CD38.
 - Refractory to IMiD.
 - Refractory to PI.
 - Refractory to IMiD and PI.
 - Refractory to IMiD, PI, and anti-CD38.
 - Refractory to last line of prior therapy.

Refractory to therapy is defined as: <25% reduction in M-protein or progression of disease during treatment or within 60 days after cessation of treatment.

